## **13. RESPONSIBILITIES**

### **13.1. Principal Investigator Responsibilities**

#### **13.1.1. Good Clinical Practice (GCP)**

The Principal Investigator will ensure that this study is conducted in accordance with the principles of the “Declaration of Helsinki” (as amended in Edinburgh, Tokyo, Venice, Hong Kong, and South Africa), International Conference on Harmonisation (ICH) guidelines, or with the laws and regulations of the country in which the research is conducted, whichever affords the greater protection to the study participant. For studies conducted under a United States IND, the Principal Investigator will ensure that the basic principles of “Good Clinical Practice,” as outlined in 21 Code of Federal Regulations (CFR 312), subpart D, “Responsibilities of Sponsors and Investigators,” 21 CFR, part 50, 1998, and 21 CFR, part 56, 1998, are adhered to. These standards are consistent with the requirements of the European Community Directive 2001/20/EC.

Since this is a “covered” clinical trial, the Principal Investigator will ensure that 21 CFR, Part 54, 1998, is adhered to; a “covered” clinical trial is any “study of a drug or device in humans submitted in a marketing application or reclassification petition participant to this part that the applicant or FDA relies on to establish that the product is effective (including studies that show equivalence to an effective product) or that make a significant contribution to the demonstration of safety.” This requires that Principal Investigators and all sub-investigators must provide documentation of their financial interest or arrangements with the Sponsor, or proprietary interests in the drug being studied. This documentation must be provided before participation of the Principal Investigator and any sub-investigator. The Principal Investigator and sub-investigator agree to notify the Sponsor of any change reportable interests during the study and for one year following completion of the study. Study completion is defined as the date that the last participant has completed the protocol defined activities.

#### **13.1.2. Institutional Review Board (IRB)/Independent Ethics Committee (IEC) Approval**

This protocol and any accompanying material to be provided to the participant (such as informed consent form, advertisements, participant information sheets, or descriptions of the study used to obtain informed consent) will be submitted by the Principal Investigator to an IRB or IEC. Approval from the IRB or IEC must be obtained before starting the study and should be documented in a letter to the Principal Investigator specifying the protocol number, protocol version, protocol date, documents reviewed, and date on which the committee met and granted the approval.

Any modifications made to the protocol after receipt of IRB or IEC approval must also be submitted to the IRB or IEC for approval before implementation.

The investigator will be responsible for the following:

- Providing written summaries of the status of the study to the IRB/IEC on an annual basis or more frequently in accordance with the requirements, policies, and procedures established by the IRB/IEC.
- Notifying the IRB/IEC of SAEs or other significant safety findings as required by procedures established by the IRB/IEC.

### **13.1.3. Informed Consent**

The Principal Investigator or designee is responsible for obtaining written informed consent from each individual participating in this study after adequate explanation of the aims, methods, objectives, and potential hazards of the study and before undertaking any study-related procedures. The Principal Investigator must utilize an IRB or IEC-approved consent form for documenting written informed consent. Each informed consent will be appropriately signed and dated by the participant and the person obtaining consent.

Participants must be re-consented to continue their participation in the study if a protocol amendment is made that substantially alters the study design or the potential risks or burden to the participant.

### **13.1.4. Confidentiality**

The Principal Investigator must assure that participants' anonymity will be strictly maintained and that their identities are protected from unauthorized parties. Only participant number (i.e., not names) and month and year of birth (as allowed) should be recorded on any form or biological sample submitted to the Sponsor, IRB or IEC, or laboratory. The Principal Investigator must keep a screening log showing codes, names, and addresses for all participants screened and for all participants enrolled in the trial.

The Principal Investigator must keep a screening log showing codes, names, and addresses for all participants screened and for all participants enrolled in the trial.

The Principal Investigator agrees that all information received from the Sponsor, including but not limited to the IB, this protocol, eCRFs, the investigational new drug, and any other study information, remain the sole and exclusive property of the Sponsor during the conduct of the study and thereafter. This information is not to be disclosed to any third party (except employees or agents directly involved in the conduct of the study or as required by law) without prior written consent from the Sponsor. The Principal Investigator further agrees to take all reasonable precautions to prevent the disclosure by any employee or agent of the study site to any third party or otherwise into the public domain.

### 13.1.5. Study Files and Retention of Records

The Principal Investigator must maintain adequate and accurate records to enable the conduct of the study to be fully documented and the study data to be subsequently verified. These documents should be classified into at least the following two categories: (1) Investigator's study file, and (2) participant clinical source documents.

The Investigator's study file will contain the IB, protocol/amendments, eCRF and query forms, IRB or IEC and governmental approval with correspondence, informed consent, drug records, staff curriculum vitae and authorization and training forms, and other appropriate documents and correspondence.

The required source data should include the following for each participant:

- participant identification (name, month and year of birth, gender);
- documentation that participant meets eligibility criteria, i.e., history, physical examination, and confirmation of diagnosis (to support inclusion and exclusion criteria);
- participation in trial (including trial number);
- trial discussed and date of informed consent;
- dates of all visits;
- documentation that protocol specific procedures were performed;
- results of efficacy parameters, as required by the protocol;
- start and end date (including dose regimen) of trial medication (preferably drug dispensing and return should be documented as well);
- record of all AEs and other safety parameters (start and end date, and preferably including causality and intensity);
- concomitant medication (including start and end date, dose if relevant; dose changes should be motivated);
- date of trial completion and reason for early discontinuation, if applicable.

All clinical study documents must be retained by the Principal Investigator until at least 2 years after the last approval of a marketing application in an ICH region (i.e., United States, Europe, or Japan) and until there are no pending or contemplated marketing applications in an ICH region; or, if no application is filed or if the application is not approved for such indication, until 2 years after the investigation is discontinued and regulatory authorities have been notified. The Principal Investigator may be required to retain documents longer if required by applicable regulatory requirements, by local

regulations, or by an agreement with the Sponsor. The Principal Investigator must notify the Sponsor before destroying any clinical study records.

Should the Principal Investigator wish to assign the study records to another party or move them to another location, the Sponsor must be notified in advance.

If the Principal Investigator cannot guarantee this archiving requirement at the study site for any or all of the documents, special arrangements must be made between the Principal Investigator and the Sponsor to store these in sealed containers outside of the site so that they can be returned sealed to the Principal Investigator in case of a regulatory audit. When source documents are required for the continued care of the participant, appropriate copies should be made for storage outside of the site.

Biological samples at the conclusion of this study may be retained in storage by the Sponsor for a period up to 10 years for purposes of this study.

### **13.1.6. Electronic Case Report Forms (eCRF)**

For each participant enrolled, an eCRF must be completed and signed by the Principal Investigator or sub-investigator (as appropriate) within a reasonable time period after data collection. This also applies to records for those participants who fail to complete the study (even during the screening period if an eCRF was initiated). If a participant withdraws from the study, the reason must be noted on the eCRF. If a participant is withdrawn from the study because of a treatment-limiting AE, thorough efforts should be made to clearly document the outcome.

### **13.1.7. Drug Accountability**

The Principal Investigator or designee (i.e., pharmacist) is responsible for ensuring adequate accountability of all used and unused investigational product including placebo. This includes acknowledgment of receipt of each shipment of study product (quantity and condition), participant dispensing records, and returned or destroyed study product. Dispensing records will document quantities received from the Sponsor and quantities dispensed to participants, including lot number, date dispensed, participant identifier number, and the initials of the person dispensing the medication.

At study initiation, the monitor will evaluate the site's standard operating procedure for investigational medicinal product disposal/destruction in order to ensure that it complies with the Sponsor requirements. Drug may be returned or destroyed on an ongoing basis during the study as appropriate. At the end of the study, following final drug inventory reconciliation by the monitor, the study site will dispose of and/or destroy all unused investigational medicinal product supplies, including empty containers, according to these procedures. If the site cannot meet the Sponsor's requirements for disposal, arrangements will be made between the site and the Sponsor or its representative for destruction or return of unused investigational medicinal product supplies.

All drug supplies and associated documentation will be periodically reviewed and verified by the study monitor over the course of the study.

### **13.1.8. Inspections**

The Principal Investigator should understand that source documents for this trial should be made available to appropriately qualified personnel from the Sponsor or its representatives, to IRBs or IECs, or to regulatory authority or health authority inspectors.

### **13.1.9. Protocol Compliance**

The Principal Investigator is responsible for ensuring the study is conducted in accordance with the procedures and evaluations described in this protocol.

## **13.2. Sponsor Responsibilities**

### **13.2.1. Protocol Modifications**

Protocol modifications, except those intended to reduce immediate risk to study participants, may be made only by the Sponsor.

### **13.2.2. Study Report and Publications**

A clinical study report will be prepared and provided to the regulatory agency(ies). The Sponsor will ensure that the report meets the standards set out in the ICH Guideline for Structure and Content of Clinical Study Reports (ICH E3). Note that an abbreviated report may be prepared in certain cases.

### **13.2.3. Posting of Information on Publicly Available Clinical Trial Registers**

Study information from this protocol will be posted on publicly available clinical trial registers before enrollment of participants begins. Results will be posted as required.

## **13.3. Joint Investigator/Sponsor Responsibilities**

### **13.3.1. Access to Information for Monitoring**

In accordance with ICH Good Clinical Practice guidelines, the study monitor must have direct access to the Principal Investigator's source documentation in order to verify the data recorded in the eCRFs for consistency.

The monitor is responsible for routine review of the eCRFs at regular intervals throughout the study to verify adherence to the protocol and the completeness, consistency, and accuracy of the data being entered on them. The monitor should have access to any participant records needed to verify the entries on the eCRFs. The Principal

Investigator agrees to cooperate with the monitor to ensure that any problems detected in the course of these monitoring visits are resolved.

### **13.3.2. Access to Information for Auditing or Inspections**

Representatives of regulatory authorities or of the Sponsor may conduct inspections or audits of the clinical study. If the Principal Investigator is notified of an inspection by a regulatory authority the Principal Investigator agrees to notify the Sponsor medical monitor immediately. The Principal Investigator agrees to provide to representatives of a regulatory agency or the Sponsor access to records, facilities, and personnel for the effective conduct of any inspection or audit.

### **13.3.3. Study Discontinuation**

The Sponsor reserves the right to terminate the study at any time. Should this be necessary, the Sponsor will arrange discontinuation procedures and notify the appropriate regulatory authority (ies), IRBs, and IECs. In terminating the study, the Sponsor and the Principal Investigator will assure that adequate consideration is given to the protection of the participants' interests.

## 15. APPENDICES

### 15.1. Appendix 1: Abbreviations and Trademarks

#### Abbreviations

AChR	Anti-acetylcholine receptor
ADA	Anti-drug antibody
AE	Adverse event
AESI	Adverse event of special interest
ALT	Alanine aminotransferase
AST	Aspartate aminotransferase
AUC (0-t)	Area under the concentration-time curve from time zero to time
AUC (0-168)	Area under the concentration-time curve from time zero to 168 hours
AZA	Azathioprine
BMI	Body mass index
BUN	Blood urea nitrogen
CI	Confidence intervals
Cmax	Maximum concentration
CO 2	Carbon dioxide
CPK	Serum creatine phosphokinase
C τ	Concentration at end of dosing interval
CV	Cardiovascular
ECG	Electrocardiogram
eCRF	Electronic case report form
FcRn	fully human anti-neonatal FC receptor
FDA	U.S. food and drug administration
FSH	Follicle stimulating hormone
GCP	Good Clinical Practice
GGT	Gamma glutamyltransferase
HBV	Hepatitis B virus
HCV	Hepatitis C virus
HIV	Human immunodeficiency virus
IB	Investigator's brochure
ICF	Informed consent form
ICH	International conference on harmonisation
IEC	Independent ethics committee
IgA	Immunoglobulin A
IgG	Immunoglobulin G
IgM	Immunoglobulin M
IND	Investigational new drug
INR	International normalized ratio
IP	Investigational product
IRB	Institutional review board

IS	Immunosuppressive
ITT	Intent to treat
IUD	Intrauterine device
IUS	Intrauterine system
IV	Intravenous
IVIG	Intravenous immunoglobulin
IWRS	Interactive Web Response System
LDH	Lactate dehydrogenase
MAD	Multiple ascending dose
MCH	Mean corpuscular hemoglobin
MCHC	Mean corpuscular hemoglobin concentration
MCV	Mean corpuscular volume
MG	Myasthenia Gravis
MG-ADL	Myasthenia Gravis-Activities of Daily Living
MGC	Myasthenia Gravis Composite
MGFA	Myasthenia Gravis Foundation of America
MG-QOL15r	Myasthenia Gravis Quality of Life
MedDRA	Medical dictionary for regulatory activities
MSDS	Material safety data sheet
MuSK	Muscle-specific kinase receptor
NAb	Neutralizing Antibody
NSAID	Non-steroidal anti-inflammatory agents
OLE	Open-label extension
PD	Pharmacodynamic
PE	Plasma exchange
pIgG	Pathogenic IgG
PIS	Post-Intervention Status
PK	Pharmacokinetic
QMG	Quantitative Myasthenia Gravis
RBC	Red blood cell
SAD	Single ascending dose
SAE	Serious adverse event
SAP	Statistical analysis plan
SC	Subcutaneous
SD	Standard deviation
SRM	Study reference manual
SUSAR	Suspected unexpected serious adverse reactions
t1/2	Elimination half-life
TB	Tuberculosis
Tmax	Time to maximum concentration
ULN	Upper limit of normal
WBC	White blood cell
WHO-DDE	World health organization drug dictionary enhanced

## Trademark Information

Trademarks of Immunovant Sciences GmbH	Trademarks not owned by Immunovant Sciences GmbH
	WinNonlin
	SAS
	FlowJo
	nSolver

## 15.2. Appendix 2: Liver Safety Required Actions and Follow up Assessments

Liver chemistry stopping criteria have been designed to assure participant safety and to evaluate liver event etiology (in alignment with the FDA Drug-induced Liver Injury: Premarketing Clinical Evaluation).

<http://www.fda.gov/downloads/Drugs/GuidanceComplianceRegulatoryInformation/Guidances/UCM174090.pdf>.

### Liver Safety Process

The procedures listed below are to be followed if a participant has ALT, bilirubin and/or INR elevations that meet the definition of a SAE (as defined in Section 11):

- Notify the medical monitor within 24 hours of learning of the abnormality to confirm follow-up.
- Complete the liver event case report forms.
- Upon completion of the safety follow-up withdraw the participant from the study unless further safety follow up is required.
- Make every reasonable attempt to have participants return to the clinic within 24 hours for repeat liver chemistries, additional testing, and close monitoring (with specialist or hepatology consultation recommended).
- Monitor participants twice weekly until liver chemistries (ALT, AST, alkaline phosphatase, bilirubin) resolve, stabilize or return to within baseline values.
- Obtain viral hepatitis serology including:
  - Hepatitis A IgM antibody.
  - Hepatitis B surface antigen and Hepatitis B Core Antibody (IgM).
  - Hepatitis C ribonucleic acid (RNA).
  - Cytomegalovirus IgM antibody.
  - Epstein-Barr viral capsid antigen IgM antibody (or if unavailable, obtain heterophile antibody or monospot testing).
  - Hepatitis E IgM antibody.
- Serum creatine phosphokinase (CPK) and lactate dehydrogenase (LDH).
- Assess eosinophilia
- Record the appearance or worsening of clinical symptoms of hepatitis (fatigue, nausea, vomiting, right upper quadrant pain or tenderness, fever, rash or eosinophilia) on the AE eCRF.
- Record use of concomitant medications, acetaminophen, herbal remedies, other over the counter medications, or putative hepatotoxins on the Concomitant Medications eCRF.

- Record alcohol use on the Liver Events eCRF.
- Anti-nuclear antibody, anti-smooth muscle antibody, Type 1 anti-liver kidney microsomal antibodies and quantitative total immunoglobulin G (IgG or gamma globulins).
- Serum acetaminophen adduct HPLC assay (quantifies potential acetaminophen contribution to liver injury in participants with definite or likely acetaminophen use in the preceding week [James, 2009]. **NOTE: not required in China** Liver imaging (ultrasound, magnetic resonance, or computerized tomography) to evaluate liver disease.

The Liver Imaging and/or Liver Biopsy eCRFs are also to be completed if these tests are performed.

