## **6.9. Stopping Criteria for Individual Participants**

### **6.9.1. Liver Chemistry Stopping Criteria**

Hepatic enzymes will be monitored in accordance with FDA drug-induced liver injury guidelines [FDA, 2009].

If the following liver test abnormalities develop, Study Treatment should be withheld immediately with appropriate clinical follow-up (including repeat laboratory tests, until a participant's laboratory profile has returned to normal/baseline status), and the event reported as a SAE:

- Alanine aminotransferase (ALT) or aspartate aminotransferase (AST)> 8 x upper limit of normal (ULN); or
- ALT or AST > 5 x ULN and persists for more than 2 weeks; or
- ALT or AST > 3 x ULN and total bilirubin > 2 x ULN or international normalized ratio (INR) > 1.5

- ALT or AST  $> 3 \times$  ULN with appearance of fatigue, nausea, vomiting, right upper quadrant pain or tenderness, fever, rash and/or eosinophilia ( $> 5\%$ ).

Rechallenge may be considered if an alternative cause for the abnormal liver tests (ALT, AST, total bilirubin) is discovered and the laboratory abnormalities resolve to normal or baseline values. The Investigator and sponsor must discuss and agree with any decision to rechallenge.

Rechallenge should not occur when the etiology of the liver test abnormalities is considered possibly drug induced.

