#### **Clinical Chemistry**

Blood urea nitrogen (BUN)	Potassium	AST (SGOT)	Total and direct bilirubin
Creatinine	Chloride	ALT (SGPT)	Uric Acid
Glucose fasting [on Day 1 (baseline) and Week 7 only]	Total carbon dioxide (CO 2 )	Gamma glutamyltransferase (GGT)	Albumin
Sodium	Calcium (corrected)	Alkaline phosphatase (ALP)	Total Protein
Serum complement (CH50, C3)	Immunoglobulin M (IgM)	Immunoglobulin A (IgA)	
Immunoglobulin G (IgG)			

Since changes in ALP, total protein and albumin level can potentially unblind the investigator to which dose the participant has been randomized to; values for ALP, total protein, and albumin levels will be blinded to the site. An unblinded Medical Monitor will review this lab data on an ongoing basis for safety.

NOTE: Details of Liver Chemistry Stopping Criteria and Follow-Up Procedures are given in Appendix 2: Liver Safety Required Actions and Follow up Assessments.

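### The Appendix 2 trigger for the liver work-up leaves out AST, although every stopping pattern in Protocol Section 6.9.1 can be met on AST

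*Protocol*

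**What the plan says.** Section 6.9.1 of the protocol lists four liver stopping patterns, and each can be met on either transaminase. The first is "Alanine aminotransferase (ALT) or aspartate aminotransferase (AST)> 8 x upper limit of normal (ULN"). The second is "ALT or AST > 5 x ULN and persists for more than 2 weeks". The third is ALT or AST above 3 x ULN together with raised bilirubin or INR. The fourth is ALT or AST above 3 x ULN with listed symptoms, rash or eosinophilia. For any of them, treatment is withheld, tests are repeated until normal or baseline, "and the event reported as a SAE".

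The clinical chemistry part of Section 8.4.4 then directs the reader onward: "Details of Liver Chemistry Stopping Criteria and Follow-Up Procedures are given in Appendix 2: Liver Safety Required Actions and Follow up Assessments". Appendix 2 opens in the same spirit: "Liver chemistry stopping criteria have been designed to assure participant safety and to evaluate liver event etiology".

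The sentence in Appendix 2 that sets the procedures in motion is narrower. They apply "if a participant has ALT, bilirubin and/or INR elevations that meet the definition of a SAE (as defined in Section 11"). Once running, they include AST: "Monitor participants twice weekly until liver chemistries (ALT, AST, alkaline phosphatase, bilirubin) resolve, stabilize or return to within baseline values".

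**The concern.** The rule that stops treatment and the rule that starts the work-up do not cover the same analytes. A participant can meet a stopping criterion on AST while nothing that the Appendix 2 trigger names is raised to a qualifying level. The site would then have an SAE and a withheld dose, but no written instruction to carry out the specified etiology work-up.

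This bears on a decision that Section 6.9.1 makes. Rechallenge may be considered if another cause is found, and should not occur if the abnormality is possibly drug induced. Appendix 2 is the only place in the protocol that specifies which tests to run to find the cause.

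**Working it through.** No figure in the plan bears on this point, so the check sets the two rules side by side.

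**Inputs**
- Trigger (Appendix 2, Liver Safety Process): ALT, bilirubin and/or INR elevations that count as an SAE under Section 11.
- Stopping patterns 1 to 4 (Section 6.9.1): all accept ALT or AST.
- SAE definition (Section 11.2): general seriousness criteria with no liver thresholds, so the reference to Section 11 does not bring AST back in.

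**Step 1. AST raised; ALT, bilirubin and INR normal.**

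| Pattern in 6.9.1 | Can AST alone meet it? | Is a trigger analyte raised? | Work-up starts, read literally? |
|---|---|---|---|
| 1: > 8 x ULN | Yes | No | No |
| 2: > 5 x ULN for more than 2 weeks | Yes | No | No |
| 3: > 3 x ULN with bilirubin > 2 x ULN or INR > 1.5 | No, needs bilirubin or INR | Yes, whenever the pattern is met | Yes |
| 4: > 3 x ULN with symptoms, rash or eosinophilia | Yes | No | No |

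Patterns 1, 2 and 4 fall outside the trigger. The permanent discontinuation rule in Section 6.9.2 does not, because it also needs raised bilirubin or INR.

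**Step 2. ALT also raised, but below any threshold.** Take AST at 9 x ULN and ALT at 1.5 x ULN as an illustration. AST meets pattern 1. ALT is elevated, but it is under the lowest 6.9.1 threshold (3 x ULN) and meets no evident criterion in Section 11.2. The trigger asks for an elevation of a named analyte that itself counts as an SAE, so on a strict reading this case is missed too. The gap is therefore any AST-driven event in which no named analyte qualifies in its own right.

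**Step 3. ALT itself meets a 6.9.1 pattern.** ALT is named in the trigger and 6.9.1 orders SAE reporting, so the work-up starts. There is no gap here.

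**Step 4. What an event in the gap still receives, and what it does not.**
- Still required: withholding, repeat tests and SAE reporting (6.9.1); automatic notice to the Medical Monitor when the SAE is entered (11.2); repeat testing and, if values do not normalise, a search for the cause where possible (8.4.4, Other tests); follow-up until resolution or stabilisation (11.7).
- Not started: the return visit within 24 hours, the twice-weekly schedule, viral serology, CPK and LDH, autoantibodies, liver imaging and the liver event eCRFs.

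**The case against.** The best case against is that the protocol, read as a whole, already links AST events to the appendix. The Section 8.4.4 note covers the stopping criteria, which include AST; the appendix opens with those criteria and follows AST. A sensible site would probably run the work-up anyway. This stands as evidence of intent, and it is a good reason to treat the omission as an oversight. It does not supply a trigger: neither the note nor the opening paragraph says when the procedures begin, and the one sentence that does leaves AST out. With about 10 to 15 sites planned, and Section 8 allowing no waivers except for immediate safety concerns, a safety trigger should not depend on each site inferring what was meant.

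It is also fair to say that the general safeguards cover much of the ground. Repeat chemistries and serial monitoring are required in general terms by 6.9.1, 8.4.4 and 11.7. A reader might count the appendix steps and infer that most of the work-up has no counterpart elsewhere. The documents do not support such a count, because it depends on whether a general or a specific counterpart is accepted. What is missing is the fixed timing and the named tests.

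Finally, the absence of a reference to 6.9.1 is not by itself the fault. Where a named analyte meets a 6.9.1 pattern, the SAE instruction in that section already leads to the trigger. The missing analyte is what opens the gap.

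**Conclusion.** The point holds as a minor defect in an operative safety rule. Three of the four stopping patterns (1, 2 and 4) can be met through AST without starting the Appendix 2 work-up as written. This rests on a literal reading of the trigger sentence.

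Two stronger readings should be resisted. A reader might infer that a participant with a stopping-level AST goes unmanaged; 6.9.1, 8.4.4, 11.2 and 11.7 show otherwise. A reader might also infer that liver findings would be lost to the analysis; SAP 10.2 already summarises and lists every AST or ALT of at least 3 x ULN, whatever the bilirubin. No efficacy result is affected.

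The documents give no event rate. Section 3.2.3.1 reports, from preliminary data in healthy participants, no clinically relevant laboratory changes on RVT-1401, and about 21 participants are planned, so such events should be rare. That limits the weight of the point but does not make the text right.

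**What to change.** Extend the Appendix 2 trigger to read: *ALT, AST, bilirubin and/or INR elevations that meet a criterion in Section 6.9.1 or 6.9.2, or that otherwise meet the SAE definition in Section 11*. The last part matters, because it keeps bilirubin-only or INR-only elevations that are SAEs but fit no pattern in 6.9.1 or 6.9.2. Nothing now covered is lost.

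The cost is one sentence in the next protocol amendment and the existing work-up for a rare AST-driven event. Scheduled assessments, Section 11.2 and the SAP need no change. The appendix's withdrawal instruction ("Upon completion of the safety follow-up withdraw the participant from the study unless further safety follow up is required") would then apply to these events as it does to ALT-driven ones. How it sits with the rechallenge allowance in 6.9.1 is a separate question that does not arise from the AST omission.
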